14. ATTACHMENTS

14.1 ATTACHMENT 1: Child Pugh Classification

Scoring System

The score employs five clinical measures of liver disease.¹ Each measure is scored 1-3, with 3 indicating most severe derangement.

Measure	1 point	2 points	3 points
Total bilirubin μmol/l (mg/dl)	<34 (≤2)	34-50 (2-3)	>50 (>3)
Serum albumin, g/l	>35	28-35	<28
PT INR	<1.7	1.71-2.30	> 2.30
Ascites	None	Mild	Moderate to Severe
Hepatic encephalopathy	None	Grade I-II (or suppressed medication)	Grade III-IV (or refractory)

Different textbooks and publications use different measures. Some older reference works substitute PT prolongation for INR.

In primary sclerosing cholangitis (PSC) and primary biliary cirrhosis (PBC), the bilirubin references are changed to reflect the fact that these diseases feature high conjugated bilirubin levels. The upper limit for 1 point is 68 μmol/l (4 mg/dl) and the upper limit for 2 points is 170 μmol/l (10 mg/dl).

Classification designation

Chronic liver disease is classified into Child Pugh class A to C, employing the added score from above.

Points	Class
5-6	A
7-9	B
10-15	C

Reference

1. Pugh RN et al. Transection of the oesophagus for bleeding oesophageal varices. Br J Surg. 1973; 60(8):646-9.

14.2 ATTACHMENT 2: Kansas City Cardiomyopathy Questionnaire

The Kansas City Cardiomyopathy Questionnaire

The following questions refer to your **heart failure** and how it may affect your life. Please read and complete the following questions. There are no right or wrong answers. Please mark the answer that best applies to you.

1. Heart failure affects different people in different ways. Some feel shortness of breath while others feel fatigue. Please indicate how much you are limited by heart failure (shortness of breath or fatigue) in your ability to do the following activities over the past 2 weeks.

Place an **X** in one box on each line

Activity	Extremely Limited	Quite a bit Limited	Moderately Limited	Slightly Limited	Not at all Limited	Limited for other reasons or did not do the activity
Dressing yourself						
Showering/Bathing						
Walking 1 block on level ground						
Doing yardwork, housework or carrying groceries						
Climbing a flight of stairs without stopping						
Hurrying or jogging (as if to catch a bus)						

2. Compared with 2 weeks ago, have your symptoms of **heart failure (shortness of breath, fatigue or ankle swelling) changed? My symptoms of **heart failure** have become ...**

Much worse	Slightly worse	Not changed	Slightly better	Much better	I've had no symptoms over
------------	----------------	-------------	-----------------	-------------	---------------------------

1. Heart failure affects different people in different ways. Some feel shortness of breath while others feel fatigue. Please indicate how much you are limited by heart failure (shortness of breath or fatigue) in your ability to do the following activities over the past 2 weeks.

the last
2 weeks

☐ ☐ ☐ ☐ ☐ ☐

3. Over the past 2 weeks, how many times did you have **swelling** in your feet, ankles or legs when you woke up in the morning?

Every morning	3 or more times a week, but not every day	1–2 times a week	Less than once a week	Never over the past 2 weeks
				

4. Over the past 2 weeks, how much has **swelling** in your feet, ankles or legs bothered you? It has been ...

Extremely bothersome	Quite a bit bothersome	Moderately bothersome	Slightly bothersome	Not at all bothersome	I've had no swelling
					

5. Over the past 2 weeks, on average, how many times has **fatigue** limited your ability to do what you want?

All of the time	Several times per day	At least once a day	3 or more times per week but not every day	1–2 times per week	Less than once a week	Never over the past 2 weeks
						

6. Over the past 2 weeks, how much has your **fatigue** bothered you? It has been ...

Extremely bothersome	Quite a bit bothersome	Moderately bothersome	Slightly bothersome	Not at all bothersome	I've had no fatigue
					

7. Over the past 2 weeks, on average, how many times has **shortness of breath** limited your ability to do what you wanted?

All of the time	Several times per day	At least once a day	3 or more times per week but not every day	1–2 times per week	Less than once a week	Never over the past 2 weeks
						

8. Over the past 2 weeks, how much has your **shortness of breath** bothered you? It has been ...

1. Heart failure affects different people in different ways. Some feel shortness of breath while others feel fatigue. Please indicate how much you are limited by heart failure (shortness of breath or fatigue) in your ability to do the following activities over the past 2 weeks.

Extremely bothersome	Quite a bit bothersome	Moderately bothersome	Slightly bothersome	Not at all bothersome	I've had no shortness of breath
					

9. Over the past 2 weeks, on average, how many times have you been forced to sleep sitting up in a chair or with at least 3 pillows to prop you up because of **shortness of breath**?

Every night	3 or more times a week, but not every day	1–2 times a week	Less than once a week	Never over the past 2 weeks
				

10. **Heart failure** symptoms can worsen for a number of reasons. How sure are you that you know what to do, or whom to call, if your **heart failure** gets worse?

Not at all sure	Not very sure	Somewhat sure	Mostly sure	Completely sure
				

11. How well do you understand what things you are able to do to keep your **heart failure** symptoms from getting worse? (for example, weighing yourself, eating a low salt diet, etc.)

Do not understand at all	Do not understand very well	Somewhat understand	Mostly understand	Completely understand
				

12. Over the past 2 weeks, how much has your **heart failure** limited your enjoyment of life?

It has extremely limited my enjoyment of life	It has limited my enjoyment of life quite a bit	It has moderately limited my enjoyment of life	It has slightly limited my enjoyment of life	It has not limited my enjoyment of life at all
				

13. If you had to spend the rest of your life with your **heart failure** the way it is right now, how would you feel about this?

Not at all satisfied	Mostly dissatisfied	Somewhat satisfied	Mostly satisfied	Completely satisfied
				

1. Heart failure affects different people in different ways. Some feel shortness of breath while others feel fatigue. Please indicate how much you are limited by heart failure (shortness of breath or fatigue) in your ability to do the following activities over the past 2 weeks.

14. Over the past 2 weeks, how often have you felt discouraged or down in the dumps because of your **heart failure**?

I felt that way all of the time	I felt that way most of the time	I occasionally felt that way	I rarely felt that way	I never felt that way
				

15. How much does your **heart failure** affect your lifestyle? Please indicate how your **heart failure** may have limited your participation in the following activities over the past 2 weeks.

Please place an **X** in one box on each line

Activity	Severely limited	Limited quite a bit	Moderately limited	Slightly limited	Did not limit at all	Does not apply or did not do for other reasons
Hobbies, recreational activities						
Working or doing household chores						
Visiting family or friends out of your home						
Intimate relationships with loved ones						

14.3 ATTACHMENT 3: Cardiac Event Recommendations and Management

Changes in BP or HR that could represent a significant safety concern should be reported to the treating physician.

If the subject meets any of the dose-limiting event criteria, the following actions on study drug should be undertaken:

1. Blood pressure (systolic) management
 - a. Minimum allowed BP 100 mmHg systolic
 - i. If <120 on antihypertensive meds, recommend reduce or discontinue
 - ii. If >120 on antihypertensive meds, no change.
2. Low blood pressure (systolic <100) management **without symptoms**
 - a. On diuretics
 - i. With edema = no change
 - ii. No edema = reduce or withdraw
 - b. On antihypertensive meds
 - i. Reduce/withdraw
 - c. On no diuretics or antihypertensive meds
 - i. No symptoms = observe
 - ii. BP <90 = reduce levosimendan dose
3. **Symptomatic** low BP management
 - a. Follow recommendations of asymptomatic scenario (above), **and**
 - i. BP <100 mild symptoms = levosimendan dose reduction
 - ii. BP <100 severe symptoms = IV phenylephrine and levosimendan dose reduction
 - iii. BP <90 on lowest dose = discontinue study
4. Sinus tachycardia at rest
 - a. HR >110 = repeat three times per protocol and obtain BP to validate
 - b. HR >110 without symptoms = in the absence of hypotension (above), observe
 - c. HR >110 with symptoms of worsening dyspnea in the absence of hypotension (above) = levosimendan dose reduction
 - d. HR >120 (validated) without symptoms = obtain ECG to determine if sinus tachycardia or atrial-fibrillation. *(If HR > 120, the treating physician should be contacted.)*
 - i. If sinus tachycardia = levosimendan dose reduction or withdraw
 - ii. If atrial fibrillation = heart rate drug management
 - e. Persistent HR >120 despite any/all above measures = discontinue study

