2.5 Investigational Product

Upon entry into the study, levosimendan was administered in open-label, intravenously at 0.075 µg/kg/min for 24 hours ±30 min, or as per directed by the treating physician. A physician was to assess the patient's safety at Week 3 and up-titrate to 0.1 µg/kg/min for 24 hours. The decision to increase the dose was to be based on the absence of disease or drug related adverse events and the investigator's discretion.

If a subject was down-titrated to 0.05 µg/kg/min in the TNX-LVO-04 study for either the Lead-In dose or during the double-blind portion of the study, the subject was to start at this dose, with the first opportunity to up-titrate following at Week 3.

All subjects will be transitioned to an oral dose of levosimendan once an informed consent form has been signed. Those currently receiving levosimendan IV weekly will return to the investigational site and receive 1mg levosimendan capsule daily for two weeks.

Subjects may then be titrated up every 2 weeks at 1mg levosimendan increments up to maximum of 4 mg daily (1mg QID), based on assessments of safety and patient's clinical response (see [Attachment 3 Cardiac Event Recommendations and Management](#)). Patients that tolerate 3 mg (1mg TID) oral levosimendan TID that have not demonstrated a 6MWD equivalent or better than the recorded 6MWD at initiation of their IV to oral levosimendan may be titrated to 4 mg (1mg QID). Patient's that experience identified safety concerns in Attachment 3 should be downtitrated at 1 mg/day increments or discontinued at the physician's discretion.

Once a patient completes the transition to oral levosimendan, all IV drug and ancillary supplies related to the administration of IV levosimendan will be returned to the central pharmacy for destruction.

At the initial visit of the IV to oral levosimendan transition, each patient will receive a supply of 1mg oral levosimendan capsules. Subsequent supplies may be shipped to the patient's home.

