14.5 ATTACHMENT 5: Patient Diary of Daily Heart Rate and Blood Pressure Readings

Week 0 through Week 2: (#) ____ capsules per day (#, as directed by physician)

Each morning, please monitor your blood pressure and heart rate. You should be sitting down and at rest **for at least five minutes** before taking your blood pressure and heart rate. The numbers you write down should be the same as those that appear on the monitor screen (do not round the numbers up or down). In the comments section, please write down anything that could have affected your reading, such as feeling unwell or changes in your medication.

NOTE: If your heart rate above 110 or your Systolic Blood Pressure is below 100, please call your doctor.

Date	Time	Heart Rate	Systolic BP (top number)	Diastolic BP (bottom number)	Study Drug # of capsules taken daily	PLEASE CHECK IF YOU ARE EXPERIENCING ANY OF THE FOLLOWING:
						 Palpitations  Light headedness  Chest pain  Worsening shortness of breath  Worsening edema (swelling)  Other _____
						 Palpitations  Light headedness  Chest pain  Worsening shortness of breath  Worsening edema (swelling)  Other _____

Week 2 through Week 4: (#) _____ capsules per day (#, as directed by physician)

Each morning, please monitor your blood pressure and heart rate. You should be sitting down and at rest **for at least five minutes** before taking your blood pressure and heart rate. The numbers you write down should be the same as those that appear on the monitor screen (do not round the numbers up or down). In the comments section, please write down anything that could have affected your reading, such as feeling unwell or changes in your medication.

NOTE: If your heart rate above 110 or your Systolic Blood Pressure is below 100, please call your doctor.

Date	Time	Heart Rate	Systolic BP (top number)	Diastolic BP (bottom number)	Study Drug # of capsules taken daily	PLEASE CHECK IF YOU ARE EXPERIENCING ANY OF THE FOLLOWING:

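### Attachment 3 gives no systolic pressure at which levosimendan is reduced in an asymptomatic, edematous patient on diuretics and no antihypertensive

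*Protocol*

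**What the plan says.** Protocol Attachment 3 (section 14.3) introduces its list as steps to take with the study drug once a dose-limiting criterion is met. The blood pressure items are these:

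- **Item 1a** states "Minimum allowed BP 100 mmHg systolic". Its sub-lines adjust only antihypertensive drugs.
- **Item 2** covers asymptomatic systolic pressure below 100. Branch 2a is for patients on diuretics: 2a(i) reads "With edema = no change", and 2a(ii), for patients without edema, cuts back or stops a drug it does not name. Branch 2b, for patients on antihypertensives, does the same. Branch 2c is headed "On no diuretics or antihypertensive meds". It says to observe, and then "BP <90 = reduce levosimendan dose".
- **Item 3** covers symptomatic patients, for example "BP <100 mild symptoms = levosimendan dose reduction".

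Elsewhere, section 2.5 says that patients with "identified safety concerns in Attachment 3 should be downtitrated at 1 mg/day increments or discontinued" at the physician's discretion. Section 2.3 has low readings followed by a symptom query that may lead to down-titration. Sections 5.4.1 and 5.4.2 (IV) and 5.5.2 and 5.5.3 (oral) permit reduction on clinical judgment. The diary in Attachment 5 says that if "your Systolic Blood Pressure is below 100, please call your doctor".

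**The concern.** Section 1.3.6 names hypotension and tachycardia as the main safety events of interest for this drug. Sections 1.3.8.3, 2.5 and 5.5.3 all send the investigator to Attachment 3 for titration and dose-limiting events. The asymptomatic levosimendan trigger at 90 mmHg is nested in one branch only, so whether a patient has a numeric trigger depends on background treatment.

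Item 2 appears to adjust background drugs first and turn to levosimendan when none is left to adjust. Patients under 2a(ii) or 2b can reach 2c once the background drug is stopped. The 2a(i) patient cannot: on the likelier reading the diuretic is kept because of the edema, and there is no antihypertensive to withdraw. Levosimendan is then the only remaining drug that item 2 could adjust, and this is the branch with no trigger for it.

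Heart rate is handled differently. Item 4d sets an asymptomatic limit (validated rate above 120) whatever the background drugs: "If sinus tachycardia = levosimendan dose reduction or withdraw".

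**Working it through.** The plan states no figure to reproduce and no arithmetic applies. The check follows one patient through Attachment 3 and then looks for a systolic dosing threshold elsewhere.

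**Patient:** asymptomatic, systolic 85 mmHg, edematous, on a diuretic, on no antihypertensive.

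| Attachment 3 item | Applies? | Result for levosimendan |
|---|---|---|
| 1a | Yes (below 100) | None; sub-lines act on antihypertensives |
| 2a(i) | Yes | No reduction; no lower bound |
| 2a(ii) | No, edema present | – |
| 2b | No antihypertensive | – |
| 2c | No, on a diuretic | – |
| 3 | No symptoms | – |

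The result is the same at any systolic value below 100. Take the patient off the diuretic, with everything else unchanged, and 2c applies: at 85 mmHg levosimendan is reduced.

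**Two readings of 2a(i).** If its object is the diuretic, the line says nothing about levosimendan. If its object is the study drug, as the Attachment's lead-in would allow, the line leaves levosimendan as it is. Neither reading yields a reduction threshold.

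**A reading that would close the gap.** One could take the 2c heading to mean lacking either class of drug, so that a patient on a diuretic alone still qualifies. This is strained, because 2a and 2b already cover patients taking those drugs.

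**Systolic numbers elsewhere:**

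- Section 3.2, criterion 11 (100 mmHg): eligibility at the start of study drug.
- Section 9.1.5 (80 mmHg or below): classification of a hypotension adverse event.
- Attachment 5 (below 100): a prompt to telephone, with no dose action.
- Sections 2.3, 2.5, 5.4.1, 5.4.2, 5.5.2 and 5.5.3: no systolic value. Section 2.3 relies on a symptom query, and this patient has no symptoms. Section 2.5 refers back to Attachment 3.
- SAP: no systolic threshold for dosing.

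**How ordinary is the branch?** Section 4.2 requires diuretics to be optimised as standard of care indicates, and section 7 has sites ask about edema at visits. The documents do not say how many patients meet all the conditions with a pressure below 90.

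**The case against.** The strongest reply is that the line in 2a(i) concerns the diuretic. The branch is defined by diuretic use, its partner 2a(ii) plainly concerns a background drug, and item 1a uses the same pattern for antihypertensives. This is the likelier reading. A reader might infer that the protocol orders levosimendan to be left alone in this patient, and so contradicts section 2.5. The documents do not establish that: the conflict exists only if the line refers to the study drug.

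Second, nothing forbids a reduction. The diary prompts a call, Attachment 3 opens by sending worrying blood pressure changes to the treating physician, and the sections listed above allow the dose to be cut. This stands. What is missing is a number, not permission.

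Third, section 9.1.5 says no single pressure defines hypotension for every subject. That passage concerns event recording, but it suggests a preference for individual judgment, and adjusting background drugs first is a coherent design. This counts against a 90 mmHg rule applied at once to every patient, which would override the order in 2a(ii) and 2b. It does not explain why 2c has a number and 2a(i) has none.

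Fourth, the clinical background is fairly reassuring. In PERSIST the largest mean systolic falls were 1.8 and 0.6 mmHg on levosimendan against 2.5 on placebo (section 1.3.4), and no HELP patient was discontinued for hypotension (section 1.3.6). Against that, hypotension in the oral studies was 6.0% against 3.4% on placebo, and doses here reach 4 mg daily, compared with 1 or 2 mg in PERSIST.

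A reader might also try to size the problem from the asymptomatic hypotensive events in the legacy pulmonary hypertension study (section 1.3.6). Those came from infusions titrated up to 0.2 µg/kg/min. The protocol gives no systolic values, edema status or diuretic use for them, so they say nothing about how often this patient occurs.

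**Conclusion.** The gap is real and narrow. An asymptomatic, edematous patient on a diuretic and no antihypertensive has no systolic value at which the protocol reduces levosimendan, while the same patient off diuretics has one at 90 mmHg. This holds on either reading of 2a(i), and depends only on the nesting in Attachment 3, whose lettering is intact in the text reviewed.

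Symptomatic patients are covered by item 3, and discretion is available throughout. The number affected is unknown and probably small. This is a cheap improvement of minor to moderate severity, not evidence that patients are left unprotected.

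One caveat: the text reviewed is protocol version 4.1, whereas SAP section 4 refers to version 5.0. Whether Attachment 3 changed in between cannot be seen.

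**What to change.** Amend Attachment 3 item 2 as follows:

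1. In 2a and 2b, name the diuretic or the antihypertensive as the drug that is kept, reduced or withdrawn.
2. Add to 2a(i) a line reducing levosimendan when systolic pressure is below 90 mmHg, the protocol's own value from 2c.
3. In 2a(ii) and 2b, apply the same line only if pressure stays below 90 after the background drug has been reduced or withdrawn. This keeps the stepwise order. A patient who meets both 2a(i) and 2b should follow the 2b order first.

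Asymptomatic patients already on the lowest dose can remain at the physician's discretion, as sections 2.5 and 5.4.1 already allow.

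The cost is a short amendment, with no new visits or procedures. The downside is a few more levosimendan reductions at asymptomatic pressures below 90, the action that the protocol already prescribes under 2c.

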14.4 ATTACHMENT 4: Study Drug Dose and Dosing Table

Preparation of the infusion

Levosimendan infusion for the 24-hour infusion (± 30 min) is prepared as follows:

- 1) for subjects < 85 kg by adding one (1) 5 mL vial of levosimendan infusion concentrate to one 250 mL infusion bag or bottle of 5% Dextrose or 0.9% Normal Saline.
- 2) for subjects ≥ 85 kg by adding two (2) 5 mL vials of levosimendan infusion concentrate to one 500 mL infusion bag or bottle of 5% Dextrose or 0.9% Normal Saline.

The concentration of the diluted infusion is about 50 $\mu\text{g/mL}$ (12.5mg/255mL in a 250mL bag; 25mg/510mL in a 500mL bag).

The diluted infusion is administered intravenously by a peripheral or central route. No other treatments should be administered via the same line.

The dosing regimen

- 1) During the Lead-In Phase, a continuous infusion of 0.1 $\mu\text{g/kg/min}$ is administered over 24 hours (± 30)
- 2) During Weeks 2 and 3, a continuous infusion of 0.075 $\mu\text{g/kg/min}$ is administered over 24 hours (± 30)
- 3) During Weeks 4 and 5, a continuous infusion of 0.1 $\mu\text{g/kg/min}$ is administered over 24 hours (± 30)

On completion of the 24-hour infusion period, the study drug infusion is switched off abruptly.

The table below, provides detailed infusion rates (for given subject weight as mL/h) for the different infusion rates of a 50 µg/mL preparation of levosimendan infusion.

Patient's weight (kg)	Infusion rate (mL/h)		
	0.1 µg/kg/min	0.075 µg/kg/min	0.05 µg/kg/min
40-44	5	4	2
45-49	5	4	3
50-54	6	5	3
55-59	7	5	3
60-64	7	6	4
65-69	8	6	4
70-74	8	7	4
75-79	9	7	5
80-84	10	8	5
85-89	10	8	5
90-94	11	8	5
95-99	11	9	6
100-104	12	9	6
105-109	13	10	6
110-114	13	10	7
115-119	14	11	7
120-124	14	11	7
125-129	15	12	8
130-134	16	12	8
135-139	16	13	8
140-144	17	13	8
145-149	17	13	9
150-154	18	14	9
155-159	19	14	9
160-164	19	15	10
165-169	20	15	10

Example for calculating infusion rates if weight is not indicated on the table above:

- For a subject weighing 38 kg subject:
- µg/kg/min infusion rate: $0.1 \times 38 \div 50 \times 60 = 5 \text{ mL/h}$
- 0.075 µg/kg/min infusion rate: $0.075 \times 38 \div 50 \times 60 = 3 \text{ mL/h}$

Dose reductions:

Patients receiving 0.10 µg/kg/min should be reduced to 0.075 µg/kg/min and patients receiving 0.075 µg/kg/min should be reduced to 0.05 µg/kg/min. Reductions below 0.05 µg/kg/min are not permitted.

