5.4 IV Levosimendan (Weekly Infusions)

5.4.1 Dosage and Administration

During the routine weekly infusion, patients will be administered a continuous intravenous (IV) infusion of a standard infusion dose of 0.075 - 0.1 µg/kg/min for 24 hours (±30 min); (levosimendan). The dose may be adjusted by the treating physician as needed (see section 6.4.2). No bolus of study drug will be administered.

Study drug concentrated solution (2.5 mg/mL), levosimendan, will be mixed with diluent and administered as weekly infusions at 0.075 µg/kg/min for 24 hrs. Patients may have a dose escalation at Weeks 3 at a rate of 0.10 µg/kg/min for 24 hrs, unless there has been a meaningful change in blood pressure or heart rate ([Attachment 4](#)) or other prohibitive rationale.

If a subject was down-titrated to 0.05 µg/kg/min in the TNX-LVO-04 study for either the Lead-In or during the double-blind portion of the study, the subject should start at this dose, with the first opportunity to up-titrate at Week 3 of the Open-Label Extension Study, TNX-LVO-05.

Note: A patient will be discontinued from the study, if the patient develops a complication or infection associated with the PICC line or port-a-cath that prevents its further use.

The infusion rate of study drug may be decreased, interrupted, or discontinued for safety reasons, according to the discretion of the investigator, as described in the following sections.

To prevent possible medication errors or miscalculations, refer to Attachment 4 of this protocol before administration of study drug to calculate the appropriate infusion rate based on the subject's body weight.

The diluted infusion is administered intravenously by a peripheral or central route. No other treatments should be administered via the same line.

The concentration of the diluted infusion is about 50 µg/mL in 5% Dextrose or 0.9% Normal Saline (12.5mg/255mL in a 250 mL bag; 25mg/510mL, 2 vials in a 500 mL bag).

The IV tubing should be primed to fill the volume to the IV entry site before starting the infusion.

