5.4.2 Dose Adjustment

The infusion rate of study drug may be decreased or interrupted as clinically warranted if the subject has hypotension, tachycardia, or signs or symptoms consistent with hypovolemia (e.g., low SBP, decreasing urine output with rising blood urea nitrogen [BUN] and serum creatinine). Record the time of discontinuation or down titration. Patients should be monitored closely until clinically stable. See [Attachment 1](#) for infusion rates and instructions on dose adjustments.

Refer to the following subsections for additional guidance on events that require study drug discontinuation or dosage adjustment, permanent discontinuation, and re-initiating study drug in subjects in whom clinical stability has been restored. In the event of a dose interruption, the infusion should be extended the amount of time of the interruption, but no more than four hours.

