7.4 Non-successful transition to oral levosimendan

Patients who do not successfully transition to oral levosimendan may re-start IV levosimendan, within a minimum of 7 days from their last dose of oral levosimendan. Once a patient re-starts IV levosimendan, they will continue to receive study drug based on the original date of entry into the TNX-LVO-05 study (i.e., final visit in the parent study, TNX-LVO-04) return to their weekly IV levosimendan dose regimen they were on prior to starting the oral transition.

Patients that re-start IV levosimendan will not have the opportunity to be given oral levosimendan in the future.

The starting dose of IV levosimendan should be at the same rate the patient was receiving prior to the transition to oral levosimendan. After re-starting IV levosimendan, the patient should be contacted by telephone after 2 weeks to assess for any safety events.

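### The three columns of the Attachment 4 infusion-rate table do not share one reference weight, so the first IV dose reduction averages about 21% instead of 25% and is only 12.5% at 70-74 kg

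*Protocol*

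**What the plan says.** Protocol Section 5.4.1 tells staff to "refer to Attachment 4 of this protocol before administration of study drug to calculate the appropriate infusion rate" from body weight. Attachment 4 (Section 14.4) then gives whole-mL/h rates for 26 bands of 5 kg, from 40-44 to 165-169 kg, in three columns: 0.1, 0.075 and 0.05 µg/kg/min. It says that the table "provides detailed infusion rates (for given subject weight as mL/h) for the different infusion rates of a 50" µg/mL preparation.

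The attachment shows its formula only in a worked case headed "Example for calculating infusion rates if weight is not indicated on the table above". A 38 kg patient is dosed at actual weight, and the result is given in whole mL/h.

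On reductions, Attachment 4 says that patients on 0.10 "should be reduced to 0.075" µg/kg/min, and those on 0.075 to 0.05, with nothing lower allowed. Section 5.4.2 gives the occasion: "The infusion rate of study drug may be decreased or interrupted as clinically warranted if the subject has hypotension, tachycardia", or signs of hypovolemia. (It points to Attachment 1 for the rates, but Attachment 1 is the Child-Pugh score; the rates are in Attachment 4.)

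IV dosing continues under the current protocol. Patients who decline the oral switch stay on it (Section 1.1), and those who fail the switch may return to it under Section 7.4: "The starting dose of IV levosimendan should be at the same rate the patient was receiving prior to the transition" to oral drug.

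**The concern.** In a banded table, one rate serves patients of different weights. That is acceptable if every column uses the same weight within the band, because the steps between dose levels then stay near their intended size. If one column uses the bottom of the band and its neighbour the top, the step between them is distorted in the same direction throughout.

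Here the affected step is the first safety reduction, from 0.10 to 0.075 µg/kg/min. Hypotension and tachycardia prompt it, and Section 1.3.6 names these as the primary safety events of interest. The protocol states the two dose levels, not a percentage; the intended cut is 1 - 0.075/0.10 = 25%. A site following the table exactly could make a much smaller cut without knowing it. The same cells govern the Week 3 increase from 0.075 to 0.1, so that step is compressed too.

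**Working it through.** **Inputs** (all from Attachment 4): the 78 printed rates; the nominal 50 µg/mL; the formula in the 38 kg example; the reduction rule. The 150 kg weight limit is from Section 3.2.

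**Formulas**
- Rate (mL/h) = dose × kg ÷ 50 × 60, rounded half-up to whole mL/h.
- Delivered dose (µg/kg/min) = mL/h × 50 ÷ 60 ÷ kg.
- First cut = 1 - (0.075 rate ÷ 0.1 rate).

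**Step 1. Reproduce the example.** At 38 kg, 0.1 × 38 ÷ 50 × 60 = 4.56, shown as 5. For 0.075 the result is 3.42, shown as 3. Both agree with the attachment.

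**Step 2. Find the reference weight for each column** (cells reproduced out of 26).

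| Weight used in the band | 0.1 | 0.075 | 0.05 |
|---|---|---|---|
| Lower (e.g. 70 in 70-74) | 26 | 18 | 26 |
| Middle (e.g. 72) | 21 | 22 | 23 |
| Upper (e.g. 74) | 16 | 26 | 20 |

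The eight 0.075 cells that miss at the lower weight are each 1 mL/h above it: 60-64, 70-74, 80-84, 105-109, 115-119, 125-129, 135-139 and 160-164 kg. All but the last are within the weight limit. Other rounding rules and a concentration of 12.5 mg/255 mL were also tried. Some fit a single column completely, but none fits all three.

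**Step 3. Compare with the formula at actual weight,** for the 111 whole-kg weights from 40 to 150.
- 0.1 column: 1 mL/h low at 28 weights, never high.
- 0.075 column: 1 mL/h high at 19 weights, never low.
- 0.05 column: 1 mL/h low at 11 weights, never high.
- Mean first cut: 21.3% from the table, 24.8% from the formula rounded to whole mL/h.

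**Step 4. First cut by band.** Of the 22 bands from 40 to 149 kg, 17 give less than 25%, 3 give 25% and 2 give more. The smallest are:
- 70-74 kg: 8 to 7 mL/h, 1 - 7/8 = 12.5%.
- 60-64 kg: 7 to 6 mL/h, 1 - 6/7 = 14.3%.
- 50-54 kg: 6 to 5 mL/h, 16.7%.
- 95-99 kg: 11 to 9 mL/h, 18.2%.

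The last two are not among the eight bands in Step 2; whole-mL rounding alone produces them. The other six bands from Step 2 give 18.8% to 23.1%.

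**Step 5. One patient.** At 70 kg, 8 mL/h delivers 8 × 50 ÷ 60 ÷ 70 = 0.095 µg/kg/min and 7 mL/h delivers 0.083. The reduced dose is 11% above its nominal 0.075. At 71-72 kg the formula gives 9 and 6 mL/h; the table gives 8 and 7.

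**Step 6. Separate rounding from the mixed weights.** With one reference weight for all columns, still in whole mL/h, the mean first cut over the 26 bands is 24.4% (lower), 24.5% (middle) or 24.5% (upper). As printed it is 21.7%. Rounding scatters the cuts around 25%; the mixed weights move them down.

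**The case against.** The case for leaving the table alone has several fair parts.

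- **The errors are small and each cell can be defended.** No rate differs from the rounded formula by more than 1 mL/h, and each is right for some weight in its band. At 67 of the 111 weights the 0.1 and 0.075 rates both agree with the formula; both differ at only three (71, 72 and 138 kg). This stands: it is an inconsistency between columns, not a set of wrong cells.
- **Rounding explains part of it.** Under one reference weight, 9 or 10 of the 22 bands would still fall below 25%, so the excess is 7 or 8 bands, not 17. At 62 kg the formula itself gives 7 and 6 mL/h. The 11% excess also arises from rounding alone at 40 and 50 kg. This stands, but rounding does not produce the one-directional shift in Steps 3 and 6.
- **The next step compensates.** At 70-74 kg the second cut, 7 to 4 mL/h, is 42.9% against a nominal 33.3%, and the full reduction from 8 to 4 is the intended 50%. This is true, but it helps only a patient who needs a second reduction.
- **How the table was built is inferred.** Different conventions fit individual columns. The supported statement is that no single convention tested fits all three.
- **Other safeguards exist.** Investigators may interrupt or stop the infusion and must monitor closely, and Section 1.3.6 reports no parent-study discontinuations for heart rate or hypotension. This bears on severity, not on whether the table delivers its stated steps.

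**Conclusion.** The concern holds. Used as written, the table makes the first IV safety reduction about 3.5 percentage points smaller on average than whole-mL rounding of the formula at actual weight would (24.8% - 21.3%). In two ordinary adult bands the cut is little more than half the nominal 25%.

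The averages weight each whole kg from 40 to 150 equally, because the documents do not give the weights of the IV patients. Delivered doses assume 50 µg/mL. At 12.5 mg/255 mL (49.0 µg/mL) they would all be about 2% lower, while the percentage cuts, being ratios of rates, would not change.

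The documents give no evidence that a patient was harmed, only patients on IV drug are exposed, and no SAP analysis depends on the table. It should be corrected because Section 5.4.1 makes it the working source for the rate and the correction is simple.

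**What to change.** Replace the table with rates from the attachment's formula at actual body weight, as its 38 kg example already does, to 0.1 mL/h where the pump allows, and state one rounding rule. Over 40-150 kg this gives a first reduction of 24.0-25.9% and delivered doses within -1.5% to +1.6% of nominal at 50 µg/mL. To avoid bedside calculation, print the rates for each whole kg.

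If 5-kg bands are kept, use the mid-band weight in all three columns to 0.1 mL/h: cuts of 24.0-25.0%, delivered doses within -5.3% to +5.6%. Do not simply change the eight 0.075 cells to lower-weight whole numbers. At 60-64 kg, 5 mL/h would deliver only 0.065-0.069 µg/kg/min.

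The cost is one replacement table and a note to sites with IV patients. The drawback is that home-infusion staff must program a decimal rate, with some risk of a decimal-point error. Pumps limited to whole mL/h would keep some rounding error, so the rounding rule must cover them.
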